5.0 Enrollment/Randomization/Blinding

Patients scheduled for open-heart surgery will be screened via StarPanel. Research personnel will request an introduction from the subject's physician. If the subject agrees to the introduction, research personnel will meet with eligible study candidates during their preoperative surgical and / or anesthesia clinic appointment or on the hospital ward. Following explanation of the protocol and documented

informed consent, patients will be randomized to 1) usual care (administration of 100% FIO₂ during surgery and 80% inspired oxygen during cardiopulmonary bypass) or 2) maintenance of physiologic oxygenation (the minimum FIO₂ required to maintain SpO₂ of 95%, but no less than that of air [21%]) during surgery. The intervention is restricted to intraoperative patient management, and upon admission to the ICU after surgery all patients will be ventilated with 40% FIO₂ or the minimum required to maintain SpO₂ 95% if greater than 40%. Regardless of treatment group, all subjects will receive 100% oxygen during induction of anesthesia until tracheal intubation and lung ventilation are verified and during transport from the operating room to the ICU. Patients, laboratory technicians, statisticians and ICU staff but not anesthesiologists, perfusionists, and respiratory therapists will be blinded to treatment group. Preoperative, intraoperative, and postoperative care will remain unaffected by inclusion in this study or by study group assignment aside from administration and monitoring of oxygenation.

The study's statistician will be responsible for centralized randomization and subject assignment based on stratification in a permuted block fashion, using a sequence of blocks with sizes either two or four, where the sizes are selected uniformly at random. Randomization will be stratified by chronic kidney disease (defined as stage 3, 4, or 5 CKD [i.e., an eGFR <60 ml/min/1.73m²]) and use of cardiopulmonary bypass during surgery.

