The DSMB will receive report on the progress, adverse events, safety endpoints, and clinical outcomes at each interim analysis from the PI and the statistician. The first planned interim analyses will occur after 20 (11.1%) subjects have been studied and discharged from the hospital following surgery. At this meeting, the DSMB will evaluate subject recruitment, the documentation of subject data, and the collection and reporting of adverse events, serious adverse events, and safety endpoints. The DSMB will also evaluate any study withdrawals, any adverse events, in-hospital all-cause mortality, and safety outcomes (stroke, TIA, or Q-wave myocardial infarction).

The second planned interim analyses will occur after 100 (50%) subjects have been studied and discharged from the hospital following surgery. At this meeting, the DSMB will evaluate any study withdrawals, any adverse events, in-hospital all-cause mortality, safety outcomes (stroke, TIA, or Q-wave myocardial infarction), and a conditional power analysis implemented by the study statistician. The conditional power analysis will assess the likelihood of rejecting the null hypotheses (for the primary endpoints of Aims 1 and 2) at the study conclusion (N=200), assuming that the effect of intervention is as large or larger than the estimated effect at the second interim analysis (N=100). To do so, the study statistician will compare mock-unblinded data (A vs. B, where it remains unknown if A or B is normoxia or

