hyperoxia). If the conditional power is less than the original target (80%), the DSMB will consider recommending an increase in the study sample size to achieve the target power. If an increased sample size is determined to be reasonable by the investigators within the study constraints including feasibility and funding, we will seek approval from the VU IRB to increase the sample size. If the sample size is increased based on the conditional power analysis, an additional interim analysis will be scheduled to occur after 200 subjects have been studied and discharged from the hospital after surgery. At this interim analysis meeting (N=200), the DSMB will evaluate safety by analyzing any study withdrawals, any adverse events, in-hospital all-cause mortality, safety outcomes (stroke, TIA, or Q-wave myocardial infarction), and the unblinded treatment effect on the primary endpoint of Aim 1 (previously only assessed in a mock-unblinded manner for the purpose of conditional power analysis). This analysis will be completed to assess safety not efficacy of the intervention. However, if the sample size is increased, then the statistical significance thresholds for the final analyses will be adjusted to preserve the overall type-I error rate at 5%. For example, if the sample size is increased to 300, then the p-value threshold at the final analysis (for the primary aim using the Wilcoxon rank sum test) will be 0.0499 to preserve the overall type-I error probability at 5%.

There will be no possibility of ending the trial early due to futility or efficacy. All investigators and research personnel (other than the study statistician at the second interim analysis) will remain blinded to treatment assignment during all interim analyses.

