difference in FMD change from baseline to ICU admission between subjects randomized to hyper-oxygenation vs. physiologic oxygenation with a standard deviation of 3.0%, with a type I error rate of 0.05 (primary analysis sub-study Aim 1). We will have 94% power to detect a correlation of 0.2 or greater between intraoperative F₂-isoprostan concentrations and postoperative FMD (primary analysis sub-study Aim 2) with standard deviation of 20 pg/ml F₂I and 10 for regression errors. We will have greater than 80% power to detect a 2% difference in FMD between patients who do and do not develop postoperative delirium in the ICU, assuming a delirium incidence of 23.4% among all ROCS trial subjects, similar to that in the Statin AKI Cardiac Surgery RCT. Sub-study Aims 1 and 2 will be completed with 80 ROCS trial subjects and sub-study Aim 3 with all 200 patients.

Randomization

The study's statistician will be responsible for centralized randomization and subject assignment based on stratification in a permuted block fashion, using a sequence of blocks with sizes either two or four, where the sizes are selected uniformly at random. Randomization will be stratified by chronic kidney disease (defined as stage 3, 4, or 5 CKD [i.e., an eGFR <60 ml/min/1.73m²]) and use of cardiopulmonary bypass during surgery. Thus, there will be four randomization strata. We use the modification of diet in renal disease formula to estimate GFR for randomization stratification. This scheme provides ample subject assignment to all strata.

Data Analysis Plan

Standard graphing and screening techniques will be used to evaluate data quality. Data include patient demographics, baseline and intraoperative clinical characteristics, treatment toxicity and clinical outcomes. Summary statistics of study arms for both numerical and categorical variables will be provided to describe the study sample. Continuous variables will be summarized with the 50th (10th, 25th, 75th, 90th) percentiles, mean and standard deviation, and categorical variables will be summarized with the counts and percentages. For outcomes measured at a single time point, comparisons across randomization groups will be implemented using the Fisher's exact test or Pearson chi-square test for categorical variables, and the Wilcoxon rank sum test or Student T-test for quantitative outcomes, as appropriate. The Clopper-Pearson and Wald methods will be used to construct 95% confidence intervals for the between group effects.

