Change in serum creatinine from baseline to postoperative day 2 (Aim 1 primary endpoint) will be compared between normoxia and hyperoxia study groups using the Wilcoxon rank sum test. Plasma concentrations of F₂-isoprostanes and isofurans (Aim 2 primary endpoint) will be compared between normoxia and hyperoxia study groups using a mixed effects regression analysis, adjusting for collection time as a categorical variable (i.e., study phase). This method allows for simultaneous evaluation of multiple correlated measurements per subject, and between-subject heterogeneity in the effects of treatment on markers of oxidative stress. Specifically, we will use a random intercept and random 'slope' for treatment allocation, indexed by study subject. Analysis of the effects of treatment on change in creatinine and on oxidative stress will be repeated separately within randomization strata.

We will evaluate treatment effect on additional markers of AKI (AKI incidence using KDIGO criteria, urine concentrations of NGAL and IGFBP-7/TEMP2, use of dialysis), delirium incidence and duration (diagnosed with CAM-ICU), and myocardial damage (quantified by measuring CK-MB on the morning of the day after surgery) as secondary analyses.

To assess effect of treatment on oxygenation and perfusion we will compare SpO₂, PO₂, cerebral oxygenation, muscle oxygenation, mixed venous hemoglobin saturation, cardiac output, and arterial lactate concentrations between normoxia and hyperoxia groups using mixed effects regression analysis as described above for plasma concentrations of F₂-isoprostanes and isofurans.

We will also compare differences in ROS production, mitochondrial function, atrial fibrillation, stroke, pneumonia, wound infection, time-to-extubation, duration of ICU stay, and in-hospital mortality as well as pain scales, depression data, and neurocognitive function between normoxia and hyperoxia groups as secondary endpoints. We will compare safety endpoints myocardial infarction, transient

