ischemic attack, and stroke between treatment groups. Similar to the primary analysis, we will implement logistic, proportional odds and linear regression analyses for binary, ordinal or highly skewed, and continuous outcomes, respectively, using a propensity score adjusted approach, if warranted. Potential impactful covariates included in these models will be specific to each outcome (for example, history of chronic obstructive pulmonary dysfunction would be appropriate covariate for time to extubation analysis).

To test the hypothesis (Endothelial function sub-study) that intraoperative physiologic oxygenation improves postoperative endothelial function (sub-study Aim 1) we will compare change from baseline in FMD (primary endpoint of Endothelial function sub-study), reactive hyperemia index, PAI-1, and E-selectin and the amplitude of endothelium-dependent vasodilation randomized subject groups in the first 80 subjects to complete the ROCS trial. The change from baseline in FMD, RHI, PAI-1, and E-selectin and the amplitude of endothelium-dependent vasodilation will be compared between oxygenation groups using Student's t-test or Mann Whitney U test. To test the hypothesis that endothelial dysfunction correlates with increased oxidative stress during cardiac surgery (sub-study Aim 2) we will compare perioperative concentrations of F₂-isoprostanes and isofurans to endothelial function assessments and plasma markers of endothelial activation at ICU admission in the first 80 subjects to complete the ROCS trial using linear regression and adjust for baseline measurements of endothelial function, and confounders such as randomized treatment group, blood transfusion, and duration of CPB. To test the hypothesis that perioperative endothelial dysfunction is associated with organ injury (sub-study Aim 3) we will compare baseline, postoperative, and change from baseline FMD, reactive hyperemia index, PAI-1, and E-selectin and the amplitude of endothelium-dependent vasodilation to markers of AKI, delirium, myocardial injury, and additional secondary endpoints using logistic, linear, or proportional odds regression as appropriate in the total cohort (N=200). We will review, interpret, and report results from sub-study Aims 1 and 2 based on statistical report from [name] but will remain blinded to treatment assignments in these 80 subjects until the entire 200 patient cohort is completed.

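### The Aim 1 primary Wilcoxon test ignores the CKD and bypass strata used in randomisation: it is valid, but a stratified version would be a cheap efficiency improvement if the strata predict creatinine change

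*Combined protocol and SAP*

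**What the plan says.** Section 5.0 states: "Randomization will be stratified by chronic kidney disease", and adds use of bypass as the second factor. The Randomization part of Section 10.0 repeats this, sets permuted blocks of two or four, and concludes: "Thus, there will be four randomization strata".

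Under Data Analysis Plan in Section 10.0, creatinine change to postoperative day 2 "will be compared between normoxia and hyperoxia study groups using the Wilcoxon rank sum test". The DSMB text in Section 6.0 names the same test in its example of a 0.0499 final threshold: "for the primary aim using the Wilcoxon rank sum test". Neither place mentions a stratified or adjusted version.

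For creatinine, the strata return only once: the analyses of creatinine change and oxidative stress "will be repeated separately within randomization strata".

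Two other places bear on the choice of test:
- The paragraph on secondary and safety endpoints in Section 10.0 opens its modelling sentence with "Similar to the primary analysis, we will implement logistic, proportional odds and linear regression analyses".
- The DSMB text says that at N=100 the "conditional power analysis will assess the likelihood of rejecting the null hypotheses" for both primary endpoints, and that for this "the study statistician will compare mock-unblinded data" labelled A and B. It does not name the test to be used there.

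**The concern.** Blocking within strata balances the arms on CKD and bypass, so between-stratum variation largely drops out of the treatment comparison. The ordinary rank-sum variance still counts that variation. If the strata are prognostic, the standard error is too large for the design, the true type I error falls below 5%, and some power is lost.

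The within-stratum repeats do not recover this. They give up to four separate results and no combined test. With assumed shares of 30% CKD and 75% bypass, the smallest stratum would hold about 200 × 0.30 × 0.25 = 15 patients.

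What is at stake is the efficiency of the main kidney result. The same test presumably feeds the N=100 step, where conditional power below 80% can lead to a request for a larger trial.

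**Working it through.** **Inputs from Section 10.0.** N = 200 (100 per arm), difference 0.15 mg/dl, SD 0.375 mg/dl, two-sided 5%. Historical mean rise 0.08 mg/dl.

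**Assumed, not in the documents.** CKD 30%, bypass 75%, strata R² from 0 to 0.20, and the error distribution.

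**1. The plan's own figure.** n per arm = 2 × (0.375/0.15)² × (1.960 + 0.842)² = 2 × 6.25 × 7.85 = 98.1, so 99 per arm or 198 in total. Power at 100 per arm is 80.7% (normal approximation) or 80.4% (t-test). The stated 80% reproduces. For a rank test with normal errors, multiplying n by 3/π gives 78.9%.

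**2. Large-sample effect of ignoring the strata.** The standardised effect is 0.4 × √50 = 2.828.
- Type I error, unstratified: 2 × [1 - Φ(1.96/√(1-R²))]
- Power, unstratified: Φ((2.828 - 1.96)/√(1-R²))
- Power, stratified: Φ(2.828/√(1-R²) - 1.96)

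At R² = 0.10, √0.90 = 0.9487. Type I error is 0.0388, and power is 0.8200 unstratified against 0.8465 stratified. At R² = 0 there is no difference.

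**3. Simulation of the actual design.** Stratified blocks of 2 or 4, normal errors, R² split equally between the two factors, 20,000 runs per cell:

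| Strata R² | Wilcoxon power | van Elteren power | Paired change (points) | Wilcoxon type I error |
|---|---|---|---|---|
| 0 | 78.5% | 78.0% | -0.41 | 5.0% |
| 0.016 | 78.5% | 78.3% | -0.26 | 4.8% |
| 0.05 | 79.1% | 80.2% | +1.09 | 4.4% |
| 0.10 | 79.9% | 82.2% | +2.35 | 3.9% |
| 0.20 | 80.7% | 86.2% | +5.49 | 3.1% |

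Van Elteren type I error stays at 4.8-5.2%. Monte Carlo SE is about 0.3 points for power, 0.15 for type I error and 0.10-0.21 for paired changes. Separate runs at R² = 0 gave losses of up to 0.9 points (78.0% against 77.1%), so the cost when the strata are not prognostic is best put at up to about one point.

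If CKD carries all of R² 0.05 or 0.10, the change is +0.9 or +2.7 points.

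**4. How large could R² be?** Assume that no stratum falls on average, so the 0.08 mg/dl mean rise limits the stratum differences.
- Equal split: [0.08/(√0.5 × 0.375 × (√(0.3/0.7) + √(0.75/0.25)))]² = 0.016
- CKD only, 30% share: [0.08/(0.375 × √(0.3/0.7))]² = 0.106
- CKD only, 20% share: [0.08/(0.375 × √(0.2/0.8))]² = 0.182

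At the last cap, simulated power is 80.6% against 85.2%, a change of +4.6 points; a second run gave +4.8. Equal-split R² 0.20 lies beyond the caps: it implies a mean fall of 0.203 mg/dl in off-pump patients without CKD.

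**5. Other error shapes.**
- t (5 df), R² 0/0.05/0.10: -0.4/+1.3/+2.8 points.
- Exponential, R² 0.108 (bypass 70%): 96.0% against 99.0%, with type I error 3.6% against 5.6% (5,000 runs).
- Lognormal (log-SD 0.8), R² 0-0.10: planned power is already 99.1-99.8% and the gain is 0.0-0.8 points. Wilcoxon type I error is 2.5% at R² 0.10.

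**The case against.** The strongest reply is that nothing here is wrong. A prespecified, valid rank test with about the stated power is a legitimate choice, and a type I error below 5% cannot produce a false claim of benefit. The gain rests on an R² that the documents do not give. If the prognostic effect is shared equally and no stratum falls on average, R² is capped at 0.016 and the stratified test gains nothing or loses slightly. A Wilcoxon test is often chosen because skew is expected, and under strong skew almost no power is at stake. Van Elteren also yields only a p-value, whereas Section 10.0 requires point estimates with 95% confidence intervals.

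All of that stands. It sets the weight of the point and shows that the replacement must name an estimator. It does not remove the mismatch between design and analysis, which is nearly free to close.

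Two further defences do not succeed. The within-stratum repeats give no single combined test. A reader might infer from "Similar to the primary analysis, we will implement logistic, proportional odds and linear regression analyses" that the primary analysis is already adjusted, but that sentence concerns secondary and safety endpoints, and the named Aim 1 test has no covariates.

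**Conclusion.** The point holds as a low-cost efficiency improvement to a valid test. Under assumed shares and normal errors, stratifying changes power by about -1 to 0 points at R² 0-0.02, by +1 to +2.5 points at R² 0.05-0.10, and by up to about +5 points if CKD alone reaches R² 0.18. Under strong skew the power gain is negligible and only the conservatism remains. The R² caps themselves rest on the assumption that no stratum falls on average.

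A reader might infer that the primary p-value is biased, that false positives are inflated, or that 200 patients are too few. The documents support none of these. Omitting prognostic strata pushes the error rate down, and the 80% figure reproduces.

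Nor should adjustment for baseline creatinine be counted in support. It is a separate, optional efficiency matter.

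**What to change.** Before unblinding, and preferably before the A-versus-B comparison at N=100, replace the Aim 1 test sentence in the Data Analysis Plan (Section 10.0) with wording such as:

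*The Aim 1 primary endpoint will be tested with a van Elteren (stratified Wilcoxon) test over the four randomisation strata as recorded at randomisation, reported with a stratified Hodges-Lehmann (or stratum-adjusted) difference in mg/dl and its 95% CI. The unstratified Wilcoxon test is a sensitivity analysis.*

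Matching edits are needed in three places:
- the conditional power step (Section 6.0, DSMB), which should name and use the same test;
- the 0.0499 example in the same text, which names the unstratified test;
- the reference to the primary analysis that opens the regression sentence for secondary and safety endpoints (Section 10.0).

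No new data are needed, because the strata are already recorded for randomisation. The cost is the rewording, reprogramming of the conditional power calculation, and up to about one point of power if the strata turn out not to be prognostic.

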4.0 Inclusion/Exclusion Criteria

Inclusion Criteria:

- Age \geq 18 years.
- Open-heart cardiac surgery, defined as surgery on the heart or aorta that requires sternotomy or thoracotomy.

Exclusion Criteria:

- Current acute coronary syndrome (defined as ST elevation myocardial infarction or non-ST elevation myocardial infarction (troponin leak within 72 hours of surgery +/- EKG changes consistent with myocardial ischemia)).
- Home supplemental oxygen use.
- Preoperative supplemental oxygen requirement to maintain SpO_2 of 92%.
- Right to left intracardiac shunt including atrial septal defect and ventricular septal defect with Cor Pulmonale.
- Carotid stenosis defined as $>50\%$ stenosis.
- Cardiac surgery that requires intraoperative circulatory arrest, such as aortic arch replacement.
- Current use of hemo- or peritoneal dialysis.
- Pregnancy

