10.0 Statistical Analysis Plan

The primary objective of the analysis will be to compare the effect of intraoperative oxygenation on oxidative damage and organ injury. The primary endpoint of Aim 1 will be change in serum creatinine from baseline (defined as the most recent creatinine measured prior to surgery) to postoperative day 2. The primary endpoint of Aim 2 will be F₂-isoprostanes/isofurans measured in plasma.

Sample Size Calculations

We calculated the subject sample size based on data from the Vanderbilt Statin AKI Cardiac Surgery RCT (PI: [name]).²⁷ Data from this study indicate that mean serum creatinine concentrations increase 0.08 ± 0.37 mg/dl from baseline to postoperative day 2. We have powered the present randomized clinical trial conservatively, particularly since consensus criteria for AKI diagnosis define AKI as a 0.3 mg/dl rise in serum creatinine from baseline to postoperative day 2.²⁹ With 200 subjects, we will have 80% power to detect a 0.15 ± 0.375 mg/dl difference in serum creatinine between groups, with a type I error rate of 5%. In addition, with 200 subjects we will have 80% power to detect a 20 ± 50 pg/ml difference in plasma F₂-isoprostanes between groups, and we observed that physiologic oxygenation was associated with 35 ± 30 pg/ml less increase in plasma concentrations of F₂-isoprostanes among pilot subjects compared to hyper-oxygenated subjects. To account for a potential dropout rate of 10%, we plan to recruit 222 subjects.

For the endothelial function sub-study, we calculated the sample size based on a prior study of patients administered an oral antioxidant, treatment improved FMD 2.3% more than placebo with a standard deviation of 2.0%.³⁰ With 80 patients, we will have greater than 80% power to detect a 2%

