Every effort will be made to avoid missing data. Any methods of missing data imputation (e.g. multiple imputation using the chained-equations method) will be used cautiously as sensitivity analyses; and the analysis of results with imputation would be interpreted in the context of corroboration with the analyses without imputation. The primary analysis will be intention-to-treat. Before data unblinding, [name] will examine any protocol deviations and identify a list of protocol violators. In addition to the intention-to-treat analysis, a secondary per-protocol analysis will be conducted.

Specific inferences on the effects of interest will be made by reporting point estimates, along with 95% confidence intervals. Hypotheses will be tested at a two-sided significance level of $\alpha=0.05$. This data analysis plan will be carried out using the statistical analysis package R (R Development Core Team).

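### The Aim 1 primary test uses baseline creatinine only by subtraction; rank-based adjustment for it would cost almost no power and could gain a few points

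*Combined protocol and SAP*

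**What the plan says.** Section 10.0 defines the Aim 1 primary endpoint as "change in serum creatinine from baseline (defined as the most recent creatinine measured prior to surgery) to postoperative day 2". Under Data Analysis Plan, this change "will be compared between normoxia and hyperoxia study groups using the Wilcoxon rank sum test". No covariates or strata are named for that test. The same paragraph adds that the creatinine analysis will be repeated separately within randomization strata.

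Other parts of the document that bear on this:

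- **Sample Size Calculations (10.0):** "With 200 subjects, we will have 80% power to detect a 0.15 ± 0.375 mg/dl difference in serum creatinine between groups". The source trial supplied the spread: "mean serum creatinine concentrations increase 0.08 ± 0.37 mg/dl from baseline to postoperative day 2".
- **Randomization (5.0 and 10.0):** permuted blocks of two or four, stratified by CKD (eGFR below 60) and by use of bypass.
- **Exclusions (4.0):** the only renal exclusion is "Current use of hemo- or peritoneal dialysis".
- **Secondary and safety endpoints (10.0):** the plan lists logistic, "proportional odds and linear regression analyses for binary, ordinal or highly skewed, and continuous outcomes", with covariates chosen per outcome. The sentence opens by likening these models to the primary analysis, although the Aim 1 primary analysis described just before it contains no regression.
- **Endothelial sub-study Aim 2 (10.0):** adjustment for the baseline measurement is named explicitly.
- **DSMB (6.0):** conditional power for the primary endpoints is computed at N=100. The example threshold of 0.0499 for an enlarged trial is tied by name to the Wilcoxon test.

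**The concern.** Subtracting baseline removes its influence only if day-2 creatinine moves one-for-one with baseline. If the slope differs from 1, change is still correlated with baseline. That correlation adds noise to the comparison, and a chance difference in baseline between arms carries through to the result. Eligibility runs from normal kidney function to stage 5 CKD without dialysis, so baseline values may vary widely, and a CKD yes/no cut leaves variation within each stratum.

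What is at stake is precision on the main kidney question, and a conditional power review at N=100 that may lead the DSMB to recommend a larger trial. The value needed for adjustment is already in hand for every patient whose change can be calculated.

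**Working it through.** **Step 1. Reproduce the plan's figure.** Inputs from section 10.0: difference 0.15 mg/dl, SD 0.375 mg/dl, two-sided alpha 0.05, 200 subjects. Equal allocation (100 per arm) is inferred from the block sizes.

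- n per arm = 2 × (1.960 + 0.842)² × 0.375² / 0.15² = 98.1, so 99, or 198 in total against 200 stated.
- Power with 100 per arm: 0.15 / (0.375 × √(2/100)) = 2.83; Φ(2.83 − 1.96) = 80.7%. The exact t calculation gives 80.4%.
- Wilcoxon test on normal data (efficiency 0.955, so 95.5 effective per arm): 0.15 / (0.375 × √(2/95.5)) = 2.76; Φ(2.76 − 1.96) = 78.9%.

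The stated 80% reproduces.

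**Step 2. What r could be.** Let rho be the correlation of baseline with day-2 creatinine and k the ratio of day-2 SD to baseline SD. Then r = (rho·k − 1) / √(1 + k² − 2·rho·k). The documents give neither input.

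- k = 1, rho = 0.8: r = −0.2 / √0.4 = −0.32.
- k = 1.25, rho = 0.8: r = 0, so nothing is gained.

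Only the size of r matters for power. The range 0 to 0.5 is an assumption.

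**Step 3. Power with and without baseline adjustment.** Simulated trials had a total of 200 patients, a 0.15 difference, SD 0.375, normal data, and blocks of two or four stratified by CKD. CKD was taken as the top 27% of baseline values (assumed). Adjustment was rank analysis of covariance on baseline.

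| r | Unadjusted Wilcoxon | Ranks adjusted for baseline | Gain (points) |
|---|---|---|---|
| 0 | 77.5% | 77.6% | about 0 |
| 0.2 | 78.6% | 79.7% | 1.1 |
| 0.3 | 78.2% and 78.5% (two runs) | 80.6% and 81.2% | 2.4 and 2.7 |
| 0.5 | 80.1% | 88.0% | 7.9 |

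Type I error was near 5%. Part of the gain would come from adjusting for CKD alone. Under simple randomization at r = 0.4, power was 78.7% unadjusted, 82.2% with CKD yes/no and 84.9% with baseline.

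**Step 4. Chance imbalance.** Under simple randomization, a two-standard-error imbalance in baseline is 2 × √(2/100) = 0.28 SD. The trial is stratified, however. With the 27% cut, the CKD split carries about 55% of baseline variance, leaving 0.28 × √(1 − 0.55) = 0.19 SD. At r = 0.3 the shift in mean change is 0.19 × 0.3 × 0.375 = 0.021 mg/dl, and 0.021 / 0.15 is about one seventh of the target.

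**Step 5. Which form of adjustment.** Simulation with 100 per arm and simple randomization at r = −0.3:

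| Errors | Wilcoxon | Linear ANCOVA | Rank ANCOVA |
|---|---|---|---|
| Normal | 78% | 84% | 82% |
| Skewed | 92% | 84% | 95% |

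With skewed errors, linear ANCOVA falls below the planned test. The rank-based form does not.

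**The case against.** The strongest reply is that nothing is broken. The test is valid, the power figure reproduces, baseline is already part of the endpoint, and randomization is stratified on kidney function. The gain depends on a correlation that the documents do not give. It may be nil, and it is only 1 to 3 points for r of 0.2 to 0.3. All of that stands, and it limits the point to efficiency.

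Three stronger readings are tempting, and the documents support none of them:

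- **That baseline is ignored and imbalance goes uncorrected.** Baseline is subtracted, CKD-stratified blocks limit imbalance, and the analysis is repeated within strata. That repeat gives separate smaller comparisons, however, and not one adjusted estimate.
- **That the gain is assured, or as large as linear ANCOVA formulas suggest.** Those formulas give 84% at r = 0.3 and 90% at r = 0.5, but they assume normal data and are not for a rank-based method.
- **That the plan clearly excludes regression for the primary endpoint.** The sentence introducing the secondary models likens them to the primary analysis and can be read either way. The text is ambiguous, and the only test actually named for Aim 1 is the unadjusted Wilcoxon.

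The objection does not remove the asymmetry. In the simulations, rank adjustment lost nothing detectable at r = 0 and gained elsewhere.

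**Conclusion.** The point holds as a low-cost improvement in efficiency, not as an error in validity, type I error or sample size. Rank-based adjustment for baseline creatinine would add about 0 points of power at r = 0, 1 at r = 0.2, 2 to 3 at r = 0.3 and 8 at r = 0.5. It would also remove a possible shift of about 0.02 mg/dl from a two-standard-error baseline imbalance at r = 0.3.

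These figures rest on an assumed range for r, an assumed 27% CKD share defined as a cut of baseline creatinine, and normal data. Actual stratification is by eGFR, which tracks creatinine imperfectly, so the true imbalance may lie between 0.19 and 0.28 SD. The simulations used rank analysis of covariance as a stand-in for the proportional odds model recommended below. The two should behave similarly as tests, but their effect measures differ.

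**What to change.** Keep change to postoperative day 2 as the endpoint. Before unblinding, and preferably before the N=100 analysis:

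1. Prespecify one primary analysis: a proportional odds model of creatinine change on arm, with baseline creatinine as a continuous covariate (log or spline) and the CKD and bypass strata as further covariates.
2. Keep the unadjusted Wilcoxon test as a sensitivity analysis.
3. Use the same adjusted test in the N=100 conditional power calculation.
4. Revise the DSMB text in section 6.0 that ties the 0.0499 example to the Wilcoxon test.
5. Reconcile the sentence likening the secondary regression models to the primary analysis with the description of the Aim 1 test.

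Do not substitute plain linear ANCOVA, which can lose power to the Wilcoxon test when change is skewed.

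The cost is wording in two sections and no new data. The main drawback is that the primary effect becomes an adjusted odds ratio, so a supporting between-arm summary in mg/dl with its 95% interval should be reported beside it.
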